In December 2017, a trial compared a chewed sublingual form of ticagrelor to standard pill form in patients with STEMI. It also showed more rapid absorption and platelet inhibition within hours of drug administration. To our knowledge, our study will be the first to compare platelet reactivity in non ST segment elevation acute coronary syndrome (NSTE-ACS) and patients with stable CAD undergoing PCI who received chewed ticagrelor.

Specific Aims:

To compare the effect of ticagrelor chewed pills with the effect of equal dose of integral pills in decreasing platelet reactivity and adverse event rates in all patients being treated for NSTE-ACS and stable coronary artery disease, undergoing percutaneous coronary intervention.

Primary objective:

Determine platelet inhibition at baseline, and early at 1 hour and 4 hours after loading dose.

Secondary objective:

Assess major adverse cardiac and cerebrovascular event (MACCE) rate at 30 days and 1 year.

1. Death;
2. Repeat myocardial infarction;
3. Need for urgent revascularization;
4. Cerebrovascular accident;
5. Rate of stent thrombosis and in-stent stenosis at 30 days and 1 year;
6. Bleeding: Defined as major, minor, or minimal bleeding based on TIMI criteria.

Hypothesis:

Chewed ticagrelor pill is superior to integral pill in decreasing platelet reactivity.

Primary Outcome Measures:

Residual platelet reactivity by Platelet Reactivity Units (PRU) VerifyNow 1 hour and 4 hours after ticagrelor loading dose (LD) and percent of patients with a high residual platelet reactivity (PRU > 208) 1 hour and 4 hours after ticagrelor LD.

Secondary Outcome Measures:

1. Bleeding events: Major, minor, minimal bleeding (TIMI criteria) events.
2. Occurrence of dyspnea and/or symptomatic bradycardia.
3. Major adverse cardiac and cerebrovascular event (MACCE) rate: Death, Myocardial infarction, Stent Thrombosis, Urgent revascularization, Cerebrovascular accident at 30 days and 1 year.

STUDY DESIGN

This will be an interventional study to evaluate the superiority of chewed ticagrelor in comparison to integral pill form. Superiority will be defined as a reduction of platelet reactivity in both groups undergoing PCI.

Study population will include 132 patients. They will be stratified into 2 groups: Patients with NSTEMI-ACS and patients with stable coronary artery disease (CAD) undergoing coronary angiography for non-urgent reasons.

Inclusion criteria:

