Patients scheduled to undergo and elective (non-urgent) coronary angiography for stable CAD who meet eligibility criteria will have blood drawn for a baseline PRU level prior to administration of the study drug. After the procedure, two subsequent blood draws will be taken at precise times: 1 hour +/-60 minutes, and 4 hours +/- 90 minutes after loading dose administration. All other procedures are considered standard of care.

Arm	Intervention/Treatment
Arm One: Chewed ticagrelor pills (Loading dose 180mg)	Drug: Ticagrelor chewed pills. The loading dose will be administered as soon as possible by hospital floor nurse or Catheterization Lab staff after a baseline PRU level is drawn. Patients will be asked to

	chew and swallow followed by 25-50mL of water.
Arm Two: Integral pill form of ticagrelor (Loading dose 180mg)	Drug: Ticagrelor integral pills. The loading dose will be administered as soon as possible by hospital floor nurse or Catheterization Lab staff after a baseline PRU level is drawn. and before the end of the PCI . Patients will swallow the loading dose followed by 25-50mL of water.

Subject will have orders to continuing ticagrelor during admission status. After the 4th hour blood draw the primary outcome will be complete. Patients will be encouraged to remain on ticagrelor with an outpatient prescription to measure secondary outcomes.

Flow Chart

Patient's EMR will be reviewed at 30 days and at 1 year to document any primary or secondary outcome measures. Duration of the study is one year.

Data collection

Baseline Characteristics	Procedure Related information	Post-procedure Related Information
Gender		
Body mass index, kg/m ²	Consenting	PRU 1 hour
Current smoker	Randomization	PRU 4 hours
Hypertension	Baseline PRU test	Length of stay
Diabetes mellitus	Loading dose administration	Date of death
Dyslipidemia	Access (femoral, Radial)	Repeat MI
Prior coronary artery disease	Start catheterization	Stent thrombosis 30 days
Prior aspirin	Culprit vessel	CVA
Prior beta-blockers	Type of stent	Urgent Revascularization
Prior statins	Number of stents	
LVEF (%)	Fluoro time/dose	
Creatinine clearance, mL/min	Contrast volume	TIMI Minimal bleeding
Hemoglobin (gr/dl)	Narcotic use	TIMI Minor bleeding
Platelet count, 1,000/mm ³		TIMI Major bleeding
Low-density lipoprotein (mg/dl)		Access site complication (hematoma, pseudoaneurysm, need for surgical or percutaneous repair)
High-density lipoprotein (mg/dl)		

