Data will be collected by the personnel delegated by the PI. Preliminary data will be analyzed after enrollment of 65 patients.

Timeline /Schedule of events

	Visit 1 Baseline	Visit 2 Procedure	Visit 3 Post Procedure	Visit 4 Discharge	Visit 5 30 day follow up- (+/- 14 d) EMR-Chart review	Visit 6 1 yr follow up- (+/- 14 d) EMR-Chart review
Inclusion/ Exclusion	X					
Informed Consent Obtained	X					
Demographics, Medical History, Con Meds	X					
Angiography /PCI Procedure		X				
Blood draw for PRU	X baseline, 1-hour and 4- hour levels can be collected before coronary angiograp hy for patients admitted to hospital floor	X	1 h after PCI 4h after PCI			

	before procedure					
MAACE Event documentation				X	X	X

Statistical Analysis

Patient characteristics will be presented as proportions for categorical variables and mean \pm standard deviation (SD) and or Median [lower quartile (01) - upper quartile (03)] for continuous variables. Comparison of categorical variables for patients who will receive integral pill form of ticagrelor and the other the chewed form will be performed using the chi-square and Fisher's exact test while the two sample t test will be done to assess differences in continuous patient characteristics. Visual displays of event free Survival and cumulative incidence curves will be generated by the Kaplan-Meier approach and event free survival among groups compared using the log rank test. In addition to time point analysis, an alternating logistic regression (ALR) will be fitted to evaluate P2Y12 reaction units (PRU) levels at baseline (before LD), 1 hour, and 4 hours. Further analysis will entail fitting both univariate and multivariate Cox proportional-hazards models to examine the association between baseline characteristics and each of outcomes: In-stent thrombosis and restenosis, MACCE, and the need for repeat revascularization within 1-year separately. All analyses will be done using SAS Version 9.4 (SAS Institute, Cary, NC) and tests performed at a 5% level of significance.

Monitoring Plan

The goal of monitoring in this study is primarily to make sure that the primary data are collected and recorded properly and consenting process was done.

The Principal Investigator will be responsible for monitoring the safety environment of the participants, and will ensure that

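### The arms are visibly different, and nothing requires whoever codes bleeding, dyspnea/bradycardia and MACCE from the chart to be unaware of the arm: a cheap improvement, for secondary outcomes only

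*Combined protocol and SAP*

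**What the plan says.** **Interventions.** In the arm table under Study procedures, patients in arm one are asked to "chew and swallow followed by 25-50mL of water". For arm two the text is "Patients will swallow the loading dose followed by 25-50mL of water". For both arms, "The loading dose will be administered as soon as possible by hospital floor nurse or Catheterization Lab staff after a baseline PRU level is drawn". No dummy or other masking step is described.

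**Outcomes.** Secondary Outcome Measures lists "Bleeding events: Major, minor, minimal bleeding (TIMI criteria) events", then "Occurrence of dyspnea and/or symptomatic bradycardia", then MACCE at 30 days and 1 year. The primary outcome is platelet reactivity read by VerifyNow at 1 and 4 hours.

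**Collection.** Under Flow Chart: "Patient's EMR will be reviewed at 30 days and at 1 year to document any primary or secondary outcome measures". After the Data collection table: "Data will be collected by the personnel delegated by the PI". That table holds randomization and loading-dose administration in its procedure column and the three TIMI bleeding grades in its post-procedure column. It has no field for dyspnea or bradycardia. The Timeline/Schedule of events has one outcome row, for MACCE, at discharge, 30 days and 1 year.

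**Oversight.** The Monitoring Plan is directed mainly at the primary data and consent. It requires prompt review of adverse events but does not mention independence or masking. Nowhere do the documents mention blinded assessors, blinded abstraction, event adjudication or a blinded analyst.

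**The concern.** The documents never call the trial open-label, but the two ways of taking the tablet cannot be concealed from the patient or from whoever gives the dose. What the study team can still control is whether the person who turns chart text into a coded outcome knows the arm, and the plan is silent on that.

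It matters most where coding needs judgement. Whether a note describes minimal bleeding or none, or dyspnea attributable to anything in particular, depends on the reader. Bleeding is at least tied to a named scale. Dyspnea/symptomatic bradycardia has no definition, time window or collection field. The stated hypothesis favours chewing, so a reader who knows the arm may resolve doubtful notes differently without intending to. That could create a safety difference that is not there or hide one that is. The title promises patient outcomes as well as platelet reactivity, so these comparisons will be read.

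**Working it through.** **What the documents settle.** The arms are visibly different, the outcomes include judgement-based items taken from the record, allocation-related items share a table with bleeding grades, and no text separates coding from allocation. The opening for bias follows from these together.

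**What they do not settle.** They give no event rates for the secondary outcomes and no basis for the degree of differential coding. There is no figure of the plan's own to reproduce, so the following is an illustration.

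*Inputs from the protocol:* 132 patients (Study Design) allocated 1:1 (Randomization), so 132/2 = 66 per arm; 5% significance level, with chi-square and Fisher's exact test named for categorical variables (Statistical Analysis). Sidedness is not stated; two-sided is assumed. I also assume that these tests would be applied to event proportions, with all patients followed.

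*Inputs assumed:* true event rate p = 10-30%, equal in both arms; relative over-recording k = 10-30% in one arm; share f of events open to judgement, either all (f = 1) or one third.

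*Formulas:*
- Recorded rate in the affected arm: p2 = p(1 + f·k). Spurious difference: d = p·f·k.
- SE = √[p(1−p)/66 + p2(1−p2)/66].
- False-positive rate, normal approximation: P(|Z + d/SE| > 1.96).
- Fisher's exact test: the two binomial distributions with n = 66 were enumerated, and the probability of all tables with p-value below 0.05 was summed.

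*Worked case, p = 20%, k = 20%, f = 1:* p2 = 0.24 and d = 0.04. SE = √(0.16/66 + 0.1824/66) = 0.072, so d/SE = 0.555. The rate is Φ(−1.405) + Φ(−2.515) = 0.080 + 0.006 = 8.6%; Fisher gives 5.8%.

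*Same case, f = 1/3:* d = 0.20 × 0.20/3 = 0.0133, SE = 0.0705, d/SE = 0.189, and the rate is 5.4%; Fisher gives 3.4%.

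| | All events affected | One third affected |
|---|---|---|
| Spurious difference, lowest (p = 10%, k = 10%) | 1 point | 0.3 point |
| Spurious difference, highest (p = 30%, k = 30%) | 9 points | 3 points |
| Apparent risk ratio (truth 1.0) | 1.10-1.30 | 1.03-1.10 |
| False positives, normal approximation | 5.4-19.4% | about 5-6.6% |
| False positives, Fisher | 2.7-15.2% | about 2.5-4.5% |

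The SE runs from about 5 to 8 points. With half of events affected, the normal-approximation range is 5.1-8.6%. Without any bias, Fisher rejects in only 2.4-3.2% of trials at these rates, so a figure below 5% in its row can still be above that test's own baseline.

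**The case against.** The strongest reply is that little is at risk. The primary objective and hypothesis concern an instrument reading, complete after the 4-hour draw. No power or event rate is claimed for the secondary outcomes. If only a minority of notes are borderline, the false-positive rate barely moves, and Fisher's test stays below 5%. All of that stands, and it limits the point to an inexpensive improvement. It does not remove it: the estimated difference is biased even where the test rarely rejects.

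A reader might infer that the same people randomise, dose, run the platelet tests and then grade outcomes. The documents do not say so. Dosing belongs to floor nurses or catheterization laboratory staff, Human Protections gives blood draws to technicians where extra draws are needed, and a delegation log is kept. The supported statement is only that overlap is not excluded and separation is not required.

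It may also be objected that chart coding of dyspnea and bradycardia rests on the general record-review sentence alone. That is correct. The absence of a dedicated field is a further gap, which the fix should close.

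Finally, clinicians who know the arm write the notes. Masking the abstractor cannot correct differences in what patients report or clinicians record. It removes only the coding step, which is the part the team controls.

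**Conclusion.** The point holds for the secondary outcomes. The plan leaves abstraction of bleeding, dyspnea/symptomatic bradycardia and MACCE open to knowledge of the arm, and the bias could run either way. Dyspnea and minimal bleeding are probably the most exposed, and death the least.

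A reader might take the top of the range, a false-positive rate near 19%, as the size of the problem. The documents do not support that. It requires a 30% event rate with every event, clear-cut ones included, recorded 30% more often in one arm, and the normal approximation rather than Fisher's test. With one third of events borderline, the rate is about 5-7%, or 2.5-4.5% with Fisher, and the spurious difference is at most 3 points. Event rate, differential recording, its direction and the borderline share are all assumptions.

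Nor do the documents support extending this to the platelet-reactivity result: VerifyNow produces a reading, not a judgement from chart text.

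**What to change.** In Data collection, state that:

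- outcome abstraction at discharge, 30 days and 1 year is done, for each patient, by an existing delegated team member who neither randomised nor dosed that patient;
- outcomes go on a form separate from the randomization and dosing items, which does not show the arm;
- the form includes a field for dyspnea/symptomatic bradycardia, now missing from the table;
- the analysis file carries the arm as A/B until endpoint coding is locked.

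This needs no extra patients, visits or blood draws, and no change to treatment. The cost is minor scheduling effort and a revised form. Masking will be partial, because notes written by unmasked clinicians may reveal the arm; the protocol should acknowledge this.

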- 4. Patients presenting with NSTEMI-ACS or stable CAD undergoing coronary angiography for urgent or non-urgent reasons.

Exclusion criteria:

1. Age <18 years or Age >90 years;
2. Known coagulopathy, bleeding diathesis, or active bleeding;
3. Known chronic therapy with clopidogrel, prasugrel, or ticagrelor;
4. Known history of intracranial bleed or intracranial neoplasm;
5. Suspected aortic dissection;
6. Severe hemodynamic instability, cardiogenic shock;
7. Life expectancy <1 year;
8. Known severe liver or renal disease (CrCl < 30, or dialysis dependent);
9. Taking drugs known to interfere with CYP3A4 metabolism (Azoles, Clarithromycin, Ritonavir, Saquinavir, Nelfinavir, Indinavir, Atazanavir);
10. Any use of GP IIb-IIIa inhibitors 48-hours before the procedure or any use during the procedure;
11. Any use of Cangrelor during or after the procedure;
12. Hemoglobin <10 g/dL, PLT <80x10⁹/L;
13. Pregnant or lactating females;

14. Known allergy to study medication;
15. Fibrinolytic use within past 48 hours;
16. Inability to give consent;
17. Known sick sinus syndrome (SSS) or high degree AV block without pacemaker protection.

Written informed consent:

Patients presenting for both urgent and elective left heart catheterization will be consented by the personnel delegated by the investigator before any study-related activity.

Randomization:

Patients will be randomized prior to PCI. Patients from each strata (NSTE—ACS, and patients with stable CAD) will be randomized in a 1:1 fashion to receive a loading dose of 180mg ticagrelor in integral pill form (swallowed) or chewed form.

Study procedures:

Patients admitted to the inpatient cardiology service with NSTE-ACS meeting eligibility criteria are often treated medically before reaching the catheterization suite for coronary angiography and possible percutaneous coronary intervention. These patients often receive the loading dose of 180mg ticagrelor on the medical floor. In order to enroll these patients, the baseline PRU level blood draw, can be obtained on the floor before that loading dose is administered. The subsequent 1-hour and 4-hour blood draws can be obtained on the medical floor or in catheterization suite.

[figure not shown]

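### The schedule of events times the 1 h and 4 h PRU draws from PCI, while the primary endpoint times them from the loading dose

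*Combined protocol and SAP*

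**What the plan says.** Three places use the loading dose as time zero:

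- The Primary objective is to "Determine platelet inhibition at baseline, and early at 1 hour and 4 hours after loading dose".
- The Primary Outcome Measures are PRU at those two times and the "percent of patients with a high residual platelet reactivity (PRU > 208) 1 hour and 4 hours after ticagrelor LD".
- Study procedures, for elective stable-CAD patients, reads "After the procedure, two subsequent blood draws will be taken at precise times: 1 hour +/-60 minutes" and then "4 hours +/- 90 minutes after loading dose administration".

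One place uses PCI as time zero. In the Timeline / Schedule of events, the PRU row under Visit 3 (Post Procedure) reads "1 h after PCI 4h after PCI".

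Three further passages bear on how far the clocks can separate:

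- In the arm table, both arms carry the same dosing instruction: "The loading dose will be administered as soon as possible by hospital floor nurse or Catheterization Lab staff", once the baseline sample is drawn. The integral-pill row adds that the dose must precede the end of the PCI. The chewed row has no such limit.
- NSTE-ACS inpatients are described as often treated before "reaching the catheterization suite for coronary angiography and possible percutaneous coronary intervention". Study procedures allows their later draws on the floor or in the catheterization suite, and the Visit 1 cell allows them before angiography. That allowance covers only patients admitted to the floor.
- The Inclusion criteria ask for NSTEMI-ACS or "stable CAD undergoing coronary angiography for urgent or non-urgent reasons". They do not require PCI.

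**The concern.** The plan has two time origins for its primary-endpoint samples, and no sentence links them. Elective patients and floor patients not sampled early are the most exposed. For elective patients, the only post-dose draws to which the schedule gives a time are the PCI-based ones, since the Visit 2 entry is an X without a time. Site staff are likely to work from the schedule. If they do, the 1 h sample can be taken at a time since dose other than the one the endpoint names, and that time will vary with the length of the procedure.

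This matters because the Background rests the case for chewing on speed of absorption and inhibition. An advantage in speed should be clearest early, so a late 1 h sample would tend to understate it. The same applies to the proportion with PRU above 208.

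Two related gaps follow from the same wording. The elective text asks for draws that are both after the procedure and 1 h after the dose, which need not be compatible. A patient who has angiography without PCI has no draw time under the Visit 3 cell, and the documents do not say whether such a patient is kept.

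**Working it through.** The plan gives no figure to reproduce here, so the check is interval arithmetic on its own times and windows.

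**Inputs**

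- Nominal times: 60 and 240 min (Primary Outcome Measures; Visit 3 cell).
- Windows (Study procedures, stated for elective patients only): 60 ± 60 = 0 to 120 min, and 240 ± 90 = 150 to 330 min after the dose. No window is stated for floor patients.
- Assumption: L is the number of minutes from the dose to the end of PCI, and a draw timed after PCI is timed from its end. The documents give no value for L, so a range is shown.

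**Formula**

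Time since dose under the Visit 3 cell = 60 + L for the first draw and 240 + L for the second.

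| L (min) | 1 h draw | In 0–120? | 4 h draw | In 150–330? |
|---|---|---|---|---|
| 0 | 60 | yes | 240 | yes |
| 30 | 90 | yes | 270 | yes |
| 60 | 120 | at limit | 300 | yes |
| 75 | 135 | no | 315 | yes |
| 90 | 150 | no | 330 | at limit |
| 120 | 180 | no | 360 | no |
| 240 | 300 | no | 480 | no |

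**Thresholds**

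- 60 + L ≤ 120 requires L ≤ 60.
- 240 + L ≤ 330 requires L ≤ 90.
- The sample labelled 1 h lies inside the 4 h window when 150 ≤ 60 + L ≤ 330, that is, when 90 ≤ L ≤ 270.

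**The elective text on its own terms**

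Let P be the minutes from the dose to the end of the procedure. A draw taken after the procedure is at least P minutes after the dose. The nominal 60 min can then be met only if P ≤ 60, and the 1 h window only if P ≤ 120. Beyond that, the sentence cannot be followed in full, whatever the schedule says.

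**The schedule on its own terms**

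Draws taken before angiography, as the Visit 1 cell allows for floor patients, cannot be timed from PCI. The PRU row therefore mixes two clocks.

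**The case against.** The strongest reply is that the endpoint is defined unambiguously from the dose in several places, and that a single cell in a post-procedure column may be shorthand. The untimed Visit 2 entry could accommodate a sample falling due during the procedure. Dosing by catheterization-lab staff is foreseen, and the integral arm may be dosed as late as just before PCI ends, so L may be short. For every L up to 60 min, both draws stay within the windows. The cell applies to both arms, so it does not by itself favour one. The documents give no PRU time course, so the direction of any bias is inferred. The flow chart is not available in the text reviewed and may show which clock was intended.

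Much of this stands. The endpoint definition is not in doubt, harm is possible rather than shown, and the effect on the arm difference is an expectation, not a result. The word describing PCI as possible is used of NSTE-ACS inpatients, not of elective patients. A patient without PCI still has a dose-based draw time under the elective text. Whether patients without PCI are analysed is a separate question.

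None of it removes the contradiction. An untimed X does not override a cell that names a time and an origin. The limit on late dosing is stated for one arm only, so L could be negative in the chewed arm, and nothing in the plan keeps L below 60 min in either arm. A flow chart could show the intention but would leave the schedule cell wrong.

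**Conclusion.** The concern holds. The Visit 3 cell conflicts with the primary objective, the primary outcome and the elective procedures text, and nothing in the documents reconciles them. This is an error in the schedule, not a missing detail, because following the cell as written can put a primary-endpoint sample at the wrong time since dose.

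Its size depends on L. There is no breach of the elective windows for L from 0 to 60 min. The 1 h draw is lost from its window above 60 min, and both draws above 90 min. These thresholds assume that the PCI clock starts at the end of PCI and that the dose is not given after it. The stratum sizes within the 132 patients are not given, so the number affected cannot be stated.

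It should be fixed. The textual conflict is certain, while its practical effect is unknown.

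**What to change.** 1. Change the Visit 3 cell to 1 h and 4 h after the loading dose, with the windows already stated for elective patients. State whether the same windows apply to floor patients.
2. Reconcile the elective sentence and the Post Procedure column heading with the dose clock, for example by saying that samples are taken at these times since dose wherever the patient then is. Study procedures already accepts draws in the catheterization suite for floor patients, and Human Protections foresees sampling from IV lines already in place.
3. Add the clock times of the loading dose and of each PRU draw to the Data collection list. The list names these items but does not say that their times are recorded.
4. In the Statistical Analysis section, keep each sample under its nominal label and flag it when its actual time since dose is outside the window, including 120–150 min and after 330 min. Report flagged samples by arm and stratum, and repeat the primary analysis without them as a sensitivity analysis only. Draw timing arises after randomization, so excluding samples on it could unbalance the arms.

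Items 1 and 2 resolve the contradiction. Items 3 and 4 are inexpensive additions that make any mistiming visible. The total cost is one table cell with a column note, one sentence, a few time fields and one analysis paragraph, with no additional draws.

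### Kaplan-Meier is the only method named for cumulative incidence curves; for any outcome that excludes death, the plan should name a competing-risk estimator (minor)

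*Combined protocol and SAP*

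**What the plan says.** The Statistical Analysis section assigns one method to two kinds of curve: "Visual displays of event free Survival and cumulative incidence curves will be generated by the Kaplan-Meier approach". It continues with "event free survival among groups compared using the log rank test". No competing-risk method is named anywhere in the document, and no rule says whether a death is censored, counted as an event or treated as competing.

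The same section plans Cox models for "In-stent thrombosis and restenosis, MACCE, and the need for repeat revascularization within 1-year separately". Thus two outcomes that do not include death are treated as time-to-event outcomes alongside the composite.

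The composite is defined under Secondary Outcome Measures, item 3: "Major adverse cardiac and cerebrovascular event (MACCE) rate: Death, Myocardial infarction, Stent Thrombosis, Urgent revascularization, Cerebrovascular accident at 30 days and 1 year". Death is a component. Secondary objective, item 5, also asks for "Rate of stent thrombosis and in-stent stenosis at 30 days and 1 year".

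Follow-up is by chart review: "Patient's EMR will be reviewed at 30 days and at 1 year". Among the clinical outcomes in the Data collection table, only death is listed with a date.

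**The concern.** One minus Kaplan-Meier estimates cumulative incidence only when no other event can remove a patient from risk for good. Someone who dies cannot later have stent thrombosis, restenosis or a repeat revascularization. If such a patient is censored, Kaplan-Meier treats them as still able to have the event and gives them the same future risk as the survivors. The curve then answers what would happen if nobody died, which is not the incidence patients experience. If the death is instead counted as an event, the curve shows event-or-death. Neither is the cumulative incidence of the named outcome.

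At stake is the accuracy of plotted 30-day and 1-year incidences for secondary outcomes, and slightly their comparison between arms or strata if mortality differs between them.

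**Working it through.** **Inputs from the documents.** There are 132 patients randomized 1:1, so about 132/2 = 66 per arm. Follow-up is 1 year. No event rate, death rate or incidence is stated, so there is no figure of the plan's to reproduce.

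**Assumed inputs.** True 1-year cumulative incidence of the non-fatal event, c = 2%, 5% or 10%. Death without that event by 1 year, d = 1% to 5%. Hazards are constant over the year.

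**Formulas.**
- Total hazard: H = -ln(1 - c - d)
- Event hazard: h = H × c/(c + d)
- One minus Kaplan-Meier, deaths censored: 1 - exp(-h)
- Aalen-Johansen targets c itself
- Upper bound, if all deaths come before any event: c/(1 - d)

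**Example, c = 10%, d = 5%.** H = -ln(0.85) = 0.1625; h = 0.1625 × 0.10/0.15 = 0.1083; 1 - exp(-0.1083) = 10.27%. The excess is 0.27 points, or 0.00268 × 66 = 0.18 of a patient per arm.

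| c | d | 1 - KM | Excess (points) | Relative excess | Excess if all deaths come first (points) |
|---|---|---|---|---|---|
| 2% | 1% | 2.01% | 0.01 | 0.5% | 0.02 |
| 2% | 5% | 2.05% | 0.05 | 2.6% | 0.11 |
| 5% | 2% | 5.05% | 0.05 | 1.0% | 0.10 |
| 5% | 5% | 5.13% | 0.13 | 2.6% | 0.26 |
| 10% | 1% | 10.05% | 0.05 | 0.5% | 0.10 |
| 10% | 5% | 10.27% | 0.27 | 2.7% | 0.53 |

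The relative excess is about d/2: deaths spread over the year are censored on average halfway through it. With d = 0 the two estimates coincide.

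**Check from the other direction.** Start from a Kaplan-Meier reading of 10% and a 1-year death risk of 5%. Then h = -ln(0.90) = 0.1054 and the death hazard is -ln(0.95) = 0.0513. The true incidence is (0.1054/0.1567) × (1 - 0.90 × 0.95) = 0.6726 × 0.145 = 9.75%. The relative excess is 10/9.75 - 1 = 2.6%, in agreement.

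**If deaths are counted as events.** With c = 10% and d = 5%, the curve would read 10% + 5% = 15%. That is a correct event-or-death figure, but not the incidence of the named outcome.

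**Between arms.** With a true incidence of 10% in both arms and deaths of 1% in one and 5% in the other, the curves would read 10.05% and 10.27%, a false gap of about 0.22 points.

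**Against sampling error.** The binomial standard error in 66 patients is sqrt(0.05 × 0.95/66) = 2.7 points at 5% and sqrt(0.10 × 0.90/66) = 3.7 points at 10%. In 4,000 simulated arms of 66, the mean excess was 0.05 points for c = 5%, d = 2%, and the two estimates were identical in 41% of arms. For c = 10%, d = 5%, the mean excess was 0.27 points. These are about 2% and 7% of the standard error.

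**MACCE.** Death is an event in the composite and so does not compete with it. Kaplan-Meier and Aalen-Johansen give the same answer at any death rate.

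**The case against.** The strongest defence is that the plan never says deaths are censored. Its sentence pairs event-free survival with cumulative incidence, and event-free survival normally counts death. If the incidence curve is just the complement of a MACCE-free survival curve, Kaplan-Meier is correct. That stands as a possible reading, but the text does not settle it. The Cox sentence takes two outcomes that exclude death as time-to-event outcomes in their own right, so curves for them are a natural expectation. For such a curve, neither way of handling deaths within Kaplan-Meier gives the stated quantity once a death precedes a later event.

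A reader might infer that every non-fatal outcome is overstated. The documents do not support that. They do not say which outcomes get a curve. For "Bleeding events: Major, minor, minimal bleeding (TIMI criteria) events", and for dyspnea and bradycardia, no time-to-event method is named; stroke and infarction enter the Statistical Analysis section only through MACCE. The 30-day and 1-year rates may also be reported as simple proportions, which do not carry this bias.

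The defence is also right on size. Life expectancy under one year, cardiogenic shock and severe hemodynamic instability are exclusions, and stable coronary disease is one of the two strata. Nothing in the documents supports a high death rate.

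**Conclusion.** The point holds as a minor correction to the stated estimator, limited to outcomes that exclude death and are given a cumulative incidence curve. In-stent thrombosis/restenosis and repeat revascularization are the plausible ones.

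Under assumed 1-year deaths of 1-5%, incidences of 2-10% and constant hazards, the overstatement is 0.01 to 0.27 percentage points. It would reach 0.53 points at c = 10%, d = 5% if every death came before any event. It is zero in any arm where no death precedes a later event. At 30 days it should be smaller, because fewer deaths have accrued. No conclusion of the trial is likely to turn on it.

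A reader might also infer that the tests are invalid. They are not: the log-rank test is specified for event-free survival, and log-rank or Cox with deaths censored remains a valid comparison of cause-specific hazards. The primary PRU outcome at 1 and 4 hours is not touched.

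**What to change.** Replace the sentence on curves with one that lists the outcomes to be plotted and states how death is handled, for example:

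> Event-free survival for death and for MACCE (including death) will be estimated by Kaplan-Meier and compared by the log-rank test. Cumulative incidence of in-stent thrombosis/restenosis and of repeat revascularization will be estimated by Aalen-Johansen, with death as a competing event.

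SAS 9.4, already named in the plan, does this in PROC LIFETEST with the EVENTCODE option. Gray's test may be added if the incidence curves are to be compared formally, but it is optional and answers a different question from a cause-specific log-rank test.

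The analysis cost is one sentence and one option. The practical cost is data: dates of the non-fatal events must be recorded at chart review. Kaplan-Meier and Cox need them too, so this is no new burden, but the Data collection table should say so. At present it gives a date only for death and lists stent thrombosis at 30 days only.
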